5.1.4 Imaging

5.1.4.1 FDG-PET/CT

5.1.4.1.1 Schedule

FDG-PET scan will be performed on patients at baseline, during cycles 1-8 if patient obtains CR or at the end of cycle 8 if no CR obtained, during cycles 9-20 if patient obtains CR or at the end

of cycle 20 if no CR obtained, during cycles 21-32 if patient obtains CR or at treatment termination. During extension phase lenalidomide, FDG-PET scans are optional for those patients that are MRD negative at the end of cycle 8 regardless of response. Patients who remain on study will have PET scans performed on an approximate annual basis during the post-maintenance follow-up phase. At PI discretion, patient may be asked to have an additional PET-CT at progression.

5.1.4.1.2 Procedures

Prior to 18F-FDG PET/CT imaging, the subject will have fasted and not received any sugar containing substance (i.e., glucose, sucrose, dextrose) for 4-6 hours. Subjects will be encouraged to drink water during this period to reduce radiation dose to the kidneys and will be asked to void prior to 18F-FDG injection.

Women of childbearing potential will have a documented report of negative pregnancy test from the CC or another accredited lab performed on the day of the scan or the day before the scan.

18F-FDG, [18F]-fluorodeoxyglucose is an FDA approved radiopharmaceutical. Immediately prior to injection, the subject's blood glucose level will be evaluated via finger stick. Non-diabetic subjects with fasting blood glucose levels above 150 mg/dl may be rescheduled at the discretion of the PI. Subjects will be asked to refrain from excessive physical exertion for the 24 hours prior to injection.

Patients will report to the NCI clinic on the day of the F-18 PET/CT scan and peripheral venous access will be obtained (most commonly via IV in the antecubital fossa). The 18F-FDG injection procedure will be injected and be followed by a ~20 ml saline (sodium chloride IV infusion 0.9% w/v) flush over a period of ~20 seconds. The injection site will be evaluated pre- and post-administration for any reaction (e.g., bleeding, hematoma, redness, or infection).

Whole body (vertex to toes) static PET/CT imaging will be performed beginning at approximately 1-hour post injection per PET/CT standard operating procedures. The patient will be instructed to maintain good hydration in order to reduce the radiation dose.

5.1.4.1.3 Research Radiation Exposure

The radiation dose from the procedure will be a maximum of 2.1 rem per year; this is within the RSC guidelines of 5.0 rem per year for adults.

5.1.4.2 DW-MRI

5.1.4.2.1 Schedule

We plan to obtain DW-MRI scans on patients on an annual basis through completion of follow up for comparison with PET/CT findings. We plan to obtain DW-MRI scans on current patients, for whom we may not have a baseline DW-MRI scan, at the same timepoints, as applicable.

5.1.4.2.2 Procedures

DW-MRI exploits differences in the diffusion of water in various tissues to internal physiology. The image contrast in reflects the difference in rate of diffusion between tissues. All attempts will be made to perform the DW-MRI scans on the same day as PET/CTs but this not mandatory. For DW-MRI, no external contrast will be used and fasting is not required. Standard clinical operating procedures will be used for image collection. DW-MRI evaluations will be considered purely exploratory.

5.1.4.2.3 Results

Patients will be informed of the results of the DW-MRI scans. But given the exploratory and research nature of the scans, these results will not be used for clinical decision-making purposes.

5.2 SAMPLE STORAGE, TRACKING AND DISPOSITION

Samples will be ordered in CRIS and tracked through a Clinical Trial Data Management system. Should a CRIS screen not be available, the CRIS downtime procedures will be followed. Samples will not be sent outside NIH without appropriate approvals and/or agreements, if required.

5.2.1 Procedures for Collecting, Processing, and Storage of Bone Marrow biopsies

- See [Appendix B](#).
- Bone marrow biopsies will be submitted in native condition to the NIH Clinical Center Department of Laboratory Medicine and handled according to routine procedures for diagnosis. Bone marrow core biopsies will be fixed and paraffin embedded for histological and immunohistochemical analysis and long-term storage. Bone marrow aspirates will be prepared according to routine procedures. Five to ten air-dried aspirate smears will be stored long-term.
- Materials for research studies will be documented on form NIH 2803-1.
- Initial processing of bone marrow aspirates for research will depend on the size of the aspirate. CD138 positive plasma cells will be isolated from a subset of these samples and stored in [name] Lab/DLM).
- For the purposes of storage, all research samples except stored serum and urine will be assigned a unique number and cataloged. Viable frozen cells will be stored in a temperature controlled, alarm secured nitrogen tank in the NIH Clinical Center Department of Hematopathology. Frozen bone marrow biopsies and processed biologic material (such as RNA and protein) will be stored at -80°C in a temperature-controlled, alarm-secured freezer. Prior to Amendment N, all research samples were stored in the laboratory of the Lymphoid Malignancies branch. As of Amendment N, these samples will be stored in a temperature controlled, alarm secured nitrogen tank/deep freezer in the NIH Department of Laboratory Medicine. For information regarding these samples, please contact [name]. at [contact] or [name], PhD at [contact].
- Frozen specimens will be wrapped in aluminum foil labeled with the patient's name and accession number, put into a resealable polyethylene freezer bag, and stored in a liquid nitrogen freezer. The liquid nitrogen freezers are monitored daily for temperature variations. A FileMaker Pro database called HP Patient Information and Specimen Inventory is used for tracking the samples.

5.2.2 Procedures for stored serum, peripheral blood, and urine specimens in the Blood Processing Core:

See [Appendix C](#) for processing of samples.

Please e-mail [contact] at least 24 hours before transporting samples (the Friday before is preferred).

For sample pickup, page [name].

For immediate help, call [contact] (main blood processing core number) or, if no answer, [contact] (main clinical pharmacology lab number).

For questions regarding sample processing, contact [contact].

- All samples sent to the Blood Processing Core (BPC) will be barcoded, with data entered and stored in the LABrador (aka LabSamples) utilized by the BPC. This is a secure program, with access to LABrador limited to defined BPC personnel, who are issued individual user accounts. Installation of LABrador is limited to computers specified by [name]. These computers all have a password restricted login screen. All BPC lab personnel with access to patient information complete the NIH online Protection of Human Subjects course.
- LABrador creates a unique barcode ID for every sample and sample box, which cannot be traced back to patients without LABrador access. The data recorded for each sample includes the patient ID, name, trial name/protocol number, time drawn, cycle time point, dose, material type, as well as box and freezer location. Patient demographics associated with the clinical center patient number are provided in the system. For each sample, there are notes associated with the processing method (delay in sample processing, storage conditions on the ward, etc.).
- Barcoded samples are stored in barcoded boxes in a locked freezer at either -20 or -80°C according to stability requirements. These freezers are located onsite in the BPC and offsite at NCI Frederick Central Repository Services in Frederick, MD. Visitors to the laboratory are required to be accompanied by laboratory staff at all times.
- Access to stored clinical samples is restricted. Samples will be stored until requested by a researcher named on the protocol. All requests are monitored and tracked in LABrador. All researchers are required to sign a form stating that the samples are only to be used for research purposes associated with this trial (as per the IRB approved protocol) and that any unused samples must be returned to the BPC. It is the responsibility of the NCI Principal Investigator to ensure that the samples requested are being used in a manner consistent with IRB approval.
- Following completion of this study, samples will remain in storage as detailed above. Access to these samples will only be granted following IRB approval of an additional protocol, granting the rights to use the material.
- If, at any time, a patient withdraws from the study and does not wish for their existing samples to be utilized, the individual must provide a written request. Following receipt of this request, the samples will be destroyed (or returned to the patient, if so requested). The PI will record any loss or unanticipated destruction of samples as a deviation. Reporting will be per the requirements of section 7.2.
- Sample barcodes are linked to patient demographics and limited clinical information. This information will only be provided to investigators listed on this protocol, via registered use of LABrador. It is critical that the sample remains linked to patient information such as race, age, dates of diagnosis and death, and histological information about the tumor, in order to correlate genotype with these variables.

5.2.3 Samples processing in the Department of Laboratory Medicine and NCI Laboratory of Pathology

- Biopsy, bone marrow or peripheral blood samples will be obtained from the Hematology Section (HS) of the NCI Laboratory of Pathology (LP) or the Hematology Section (HS)

of the DLM, CC.

- Samples are coded by the LP HS, DLM HS or [name] Lab. Tissue sections, or peripheral blood samples will be obtained and stored in the [name] lab without any personal identifiers and will be labeled with the anonymous LP HS or DLM HS accession ID number.
- The relationship between the accession ID number and the patient clinical information will be stored in a secure database that is maintained and regularly backed up by [name].
- The [name] laboratory may prepare tissue lysates, RNA and DNA from each sample. Samples, lysates and derived biologic molecules will be stored in Eppendorf tubes marked with the sample accession ID number in locked -80° C freezers in the [name] laboratory.

5.3 SAMPLES FOR GENETIC/GENOMIC ANALYSIS

5.3.1 Description of the scope of genetic/genomic analysis

Genomic testing will be done as described in Section **5.1.1**.

5.3.2 Description of how privacy and confidentiality of medical information/biological specimens will be maximized

Confidentiality for genetic samples will be maintained as described in Section **5.2**. In addition, a Certificate of Confidentiality has been obtained for this study.

5.3.3 Management of Results

Subjects will be contacted if a clinically actionable gene variant is discovered. Clinically actionable findings for the purpose of this study are defined as disorders appearing in the American College of Medical Genetics and Genomics recommendations for the return of incidental findings that is current at the time of primary analysis. (A list of current guidelines is maintained on the CCR intranet:

<https://ccrod.cancer.gov/confluence/display/CCRCRO/Incidental+Findings+Lists>).

Subjects will be contacted at this time with a request to provide a blood sample to be sent to a CLIA certified laboratory within the NIH or as a send-out test to another CLIA certified lab.

This is the only time during the course of the study that incidental findings will be returned. No interrogations regarding clinically actionable findings will be made after the primary analysis.

5.3.4 Genetic counseling

If the research findings are verified in the CLIA certified lab, the subject will be referred to a genetic healthcare provider within the NIH for the disclosure of the results. These activities will be funded by the Center for Cancer Research.

6 DATA COLLECTION AND EVALUATION

6.1 DATA COLLECTION

The PI will be responsible for overseeing entry of data into an in-house password protected electronic system (C3D) and ensuring data accuracy, consistency and timeliness. The principal investigator, associate investigators/research nurses and/or a contracted data manager will assist

with the data management efforts. All data obtained during the conduct of the protocol will be kept in secure network drives or in approved alternative sites that comply with NIH security standards. Primary and final analyzed data will have identifiers so that research data can be attributed to an individual human subject participant.

All AEs, including clinically significant abnormal findings on laboratory evaluations, regardless of severity, will be followed from Study Day 1 through 30 days after the last dose of study drug or until return to baseline or stabilization of event, whichever is later, or until the subject comes off-study. Beyond 30 days after the last intervention, only adverse events which are serious and related to the study intervention need to be recorded.

An abnormal laboratory value will be considered an AE if the laboratory abnormality is characterized by any of the following:

- Results in discontinuation from the study
- Is associated with clinical signs or symptoms
- Requires treatment or any other therapeutic intervention
- Is associated with death or another serious adverse event, including hospitalization.
- Is judged by the Investigator to be of significant clinical impact
- If any abnormal laboratory result is considered clinically significant, the investigator will provide details about the action taken with respect to the test drug and about the patient's outcome.

End of study procedures: Data will be stored according to HHS, FDA regulations and NIH Intramural Records Retention Schedule as applicable.

Loss or destruction of data: Should we become aware that a major breach in our plan to protect subject confidentiality and trial data has occurred, this will be reported expeditiously per the requirements in section 7.2.

6.1.1 Long-term follow-up

When patients enter the long-term follow-up period, the following data will be collected:

- adverse events related to Carfilzomib
- survival status which will be collected by phone or clinic visit
- additional cancer therapy received

6.1.2 Record Keeping

Complete records must be maintained on each patient; these records will consist of the hospital chart as well as any other outside information obtained from outside laboratories, radiology reports, or physician's records. All relevant data will also be entered on a computer database from which formal analyses are done. The primary source documentation will include patient eligibility data, patient history, flow sheets (including specialty forms for pathology, radiology, or surgery), an off-study summary sheet, and a final assessment by the treating physician.

6.1.3 Forwarding of Patient Data from Other Institutions

Either due to extenuating medical circumstances or for convenience, some patients may elect to have certain routine laboratory studies or protein marker analyses performed at an outside institution between scheduled interval visits to the CRC for this protocol. These results will be forwarded to the Myeloma Research Nurse, data will be entered into the study database and filed in the medical record. Additional blood or tissue samples/results drawn on patients enrolled in

this protocol between scheduled visits may be forwarded and entered into the database as indicated.

6.2 DATA SHARING PLANS

6.2.1 Human Data Sharing Plan

What data will be shared?

I will share human data generated in this research for future research as follows:

Coded, linked data in an NIH-funded or approved public repository. Coded, linked data in BTRIS (automatic for activities in the Clinical Center)

Identified or coded, linked or identified data with approved outside collaborators under appropriate agreements. **How and where will the data be shared?**

Data will be shared through:

An NIH-funded or approved public repository. Insert name or names:
ClinicalTrials.gov, dbGAP

BTRIS (automatic for activities in the Clinical Center)

Approved outside collaborators under appropriate individual agreements.

Publication and/or public presentations.

When will the data be shared?

At the time of publication or shortly thereafter.

6.2.2 Genomic Data Sharing Plan

Unlinked genomic data will be deposited in public genomic databases such as dbGaP in compliance with the NIH Genomic Data Sharing Policy.

6.3 RESPONSE CRITERIA

6.3.1 Timing

Response assessments will be performed Day 1 of every cycle during Cycles 1-8 and every third cycle during Cycles 9-20: Cycles 9, 12, 15 and 18 and every third cycle during Cycles 21-32: Cycles 21, 24, 27, 30 and end of 32.

6.3.2 Disease Parameters

- Measurable is defined as any of the following: serum M-protein is ≥ 1 g/dL or "measurable" urine M-spike is ≥ 200 mg/24 hours or serum kappa or lambda FREE light chain of 10 mg/dL along with an abnormal kappa to lambda free light chain ratio.
- The serum free light chain (FLC) assay is of particular use in monitoring response to therapy in patients who have oligo-secretory disease. When using this assay, it is important to note that the FLC levels vary considerably with changes in renal function and do not solely represent monoclonal elevations. Thus both the level of the involved and the uninvolved FLC isotype (i.e., the involved/uninvolved ratio or involved-uninvolved difference) should be considered in assessing response. The serum FLC assay should be used in assessing response only if the baseline serum and/or urine M proteins are not "measurable" by traditional criteria (serum M protein ≥ 1 gm/dL and/or urine M

protein ≥ 200 mg/24), and the baseline level of the involved FLC is ≥ 10 mg/dL and clonal (abnormal ratio). Patients included on the study on the basis of FLC alone (i.e., no measurable serum/urine) should be the only ones who are evaluated using FLC response criteria. The others should follow usual criteria and ignore FLC results.

- In order to be classified as a hematologic response, confirmation of serum monoclonal protein, serum immunoglobulin free light chain (when primary determinant of response) and urine monoclonal protein (when primary determinant of response) results must be made by verification on two consecutive determinations.
- Caution must be exercised to avoid rating progression or relapse on the basis of variation of radiological technique alone. Compression fracture does not exclude continued response and may not indicate progression. When progression is based on skeletal disease alone, it should be discussed with the PI before removing the patient from the study.
- Appearance of monoclonal or oligoclonal bands that are different from original isotype may not be defined as “relapse from CR”. Oftentimes, such bands may indicate fluctuations in immunological parameters that are not reflective of MM disease. In these situations, immunofixation and electrophoresis will be interpreted by the clinician before being labeled as “relapse”[\(30\)](#).

6.3.3 Response Criteria from International Myeloma Working Group Criteria[\(31\)](#) and addition of nCR category[\(6, 21\)](#):

6.3.3.1 Evaluation of Response Criteria

- **Stringent Complete Response (sCR)**

Complete Response as defined below plus:

Normal FLC ratio and absence of clonal cells in bone marrow by immunohistochemistry or immunofluorescence (presence/ absence of clonal cells is based on the kappa/ lambda ratio.

- **Complete Response (CR)**

Negative immunofixation on the serum and urine and disappearance of any soft tissue plasmacytomas and $\leq 5\%$ plasma cells in bone marrow

- **Near Complete Response (nCR)**

Defined as absence of myeloma protein on electrophoresis, independent of immunofixation status[\(6, 21\)](#)

- **Very Good Partial Response (VGPR)**

Serum and urine M-protein detectable by immunofixation but not on electrophoresis or 90% or greater reduction in serum M-protein plus urine M-protein level < 100 mg per 24h. If the serum and urine M-protein are unmeasurable, a $\geq 90\%$ decrease in the difference between involved and uninvolved FLC levels is required in place of the M-protein criteria.

- **Partial Response (PR)**

$\geq 50\%$ reduction of serum M-protein and reduction in 24-h urinary M-protein by $\geq 90\%$ or to < 200 mg per 24h. If the serum and urine M-protein are unmeasurable, a $\geq 50\%$ decrease in the difference between involved and uninvolved FLC levels is required in place of the M-protein criteria

- **Stable Disease (SD)**

Not meeting criteria for CR, VGPR, PR or progressive disease. All categories also require no known evidence of progressive or new bone lesions if radiographic studies

were performed. Radiographic studies are not required to satisfy these response requirements.

- **Progressive disease (PD)**

Requires any one or more of the following:

Increase of $\geq 25\%$ from lowest response value in the following on 2 consecutive measurements:

- Serum M-component and/or (the absolute increase must be ≥ 0.5 g/dl). The serum M-component increases of ≥ 1 gm/dl are sufficient to define relapse if starting M-component is ≥ 5 g/dl.
- Urine M-component and/or (the absolute increase must be ≥ 200 mg/24h
- Only in patients without measurable serum and urine M-protein levels: the difference between involved and uninvolved FLC levels. The absolute increase must be >10 mg/dl.
- Bone marrow plasma cell percentage: the absolute % must be $\geq 10\%$
- Definite development of new bone lesions or soft tissue plasmacytomas or definite increase in size of existing bone lesions or soft tissue plasmacytomas
- Development of hypercalcemia that can be attributed solely to the plasma cell proliferative disorder

- **Relapse from CR**

Any one or more of the following:

- Reappearance of serum or urine M-protein by immunofixation or electrophoresis. (Appearance of monoclonal or oligoclonal bands that are different from original isotype may not be defined as “relapse from CR”. Oftentimes, such bands may indicate fluctuations in immunological parameters that are not reflective of MM disease. In these situations, immunofixation and electrophoresis will be interpreted by the clinician before being labeled as “relapse”. ([32](#), [33](#)))
- Development of $\geq 5\%$ plasma cells in the bone marrow
- Appearance of any other sign of progression (i.e., new plasmacytoma, lytic bone lesion, hypercalcemia)

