2 ELIGIBILITY ASSESSMENT AND ENROLLMENT

2.1 ELIGIBILITY CRITERIA

2.1.1 Inclusion Criteria

2.1.1.1 Newly diagnosed patients with histologically confirmed Multiple Myeloma (MM based on the following criteria:

- a) Clonal plasma cells in the bone marrow
- b) Measurable disease within the past 4 weeks defined by any one of the following:
 - Serum monoclonal protein ≥ 1.0 g/dL
 - Urine monoclonal protein >200 mg/24 hour
 - Serum immunoglobulin free light chain > 10 mg/dL AND abnormal kappa/lambda ratio
- c) Evidence of underlying end organ damage attributed to underlying plasma cell proliferative disorder meeting at least one of the following:
 - Hypercalcemia: serum calcium ≥ 2.65 mmol/L
 - Renal Insufficiency: serum creatinine > 2.0 mg/dL
 - Anemia: hemoglobin value <10 g/dL or 2 g/dL $<$ normal reference
 - Bone disease: lytic lesions, severe osteopenia or pathological fractures

2.1.1.2 Creatinine Clearance ≥ 60 ml/min. CrCl will be calculated by Cockcroft-Gault method. $\text{CrCl (calculated)} = (140 - \text{Age}) \times \text{Mass (in kilograms)} \times [0.85 \text{ if Female}] / 72 \times \text{Serum Creatinine (in mg/dL)}$. If calculated CrCl based on Cockcroft-Gault method is <60 mL/min, patient will have a 24 hr urine collection to measure CrCl. The measured CrCl must also be ≥ 60 ml/min.

2.1.1.3 Age ≥ 18 years. Because no dosing or adverse event data are currently available on the use of carfilzomib in combination with lenalidomide in patients <18 years of age, children are excluded from this study, but will be eligible for future pediatric trials.

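### CR and nCR carry no free-light-chain criterion, so a patient followed by FLC only can be scored CR without meeting PR, or meet nCR before treatment

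*Combined protocol and SAP*

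**What the plan says.** Section 2.1.1 requires "Measurable disease within the past 4 weeks defined by any one of the following", and one of the three alternatives is "Serum immunoglobulin free light chain > 10 mg/dL AND abnormal kappa/lambda ratio". No serum or urine M-protein is needed on that route. Section 6.3.2 then states that patients entered on FLC alone "should be the only ones who are evaluated using FLC response criteria"; all others are told to disregard FLC.

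Section 6.3.3.1 follows this through for some categories only. For VGPR and PR, when M-protein is unmeasurable, a fall of at least 90% or 50% respectively applies: a "decrease in the difference between involved and uninvolved FLC levels is required in place of the M-protein criteria". PD also has an FLC limb. sCR adds "Normal FLC ratio and absence of clonal cells in bone marrow by immunohistochemistry or immunofluorescence" to CR.

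CR itself is "Negative immunofixation on the serum and urine and disappearance of any soft tissue plasmacytomas", with marrow plasma cells at or below 5%. nCR is "Defined as absence of myeloma protein on electrophoresis, independent of immunofixation status". Neither mentions FLC.

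ORR in 6.3.7 is the sum of PR, VGPR and CR. Section 10.3.1 plans to report VGPR+CR and CR alone, each with a two-sided 95% confidence interval.

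**The concern.** For a patient whose only disease marker is FLC, the two M-protein-based categories above VGPR do not look at that marker. Such a patient can reach CR while failing the FLC test for PR, so the response scale is no longer ordered. The same patient can satisfy nCR with no change from baseline.

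At stake is the meaning of the secondary response rates. CR feeds ORR, VGPR+CR and CR alone, and duration of response (6.3.4) runs from the time the best-response criteria are met. There is also a wording conflict. Section 6.3.2 tells patients with measurable M-protein to disregard FLC, while sCR requires a normal FLC ratio of everyone.

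**Working it through.** **The plan's own figure.** Section 1.2.10 reports best response in the first 20 patients as 15 nCR/sCR, 2 VGPR, 2 PR and 1 SD. 15 + 2 + 2 = 19, and 19/20 = 95%, the ORR stated there. VGPR and PR supply only 4 of the 19, so 95% is reached only by counting the whole nCR/sCR group, although 6.3.7 does not name nCR. The split between nCR and sCR is not given.

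**The rules side by side (6.3.3.1), for a patient followed by FLC only.**

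| Category | FLC condition | Other conditions |
|---|---|---|
| sCR | normal ratio | CR, and no clonal marrow cells |
| CR | none | immunofixation negative in serum and urine, no plasmacytoma, marrow plasma cells ≤5% |
| nCR | none | nothing visible on electrophoresis |
| VGPR | difference down ≥90% | none |
| PR | difference down ≥50% | none |
| SD | none | not CR, VGPR, PR or PD; nCR is not excluded |

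Neither CR nor nCR requires that PR or VGPR also be met.

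**Applying them.** Assumed values: FLC difference 14 mg/dL at baseline, abnormal ratio, no measurable M-protein. Fall = 1 − current/14.

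1. Before the first dose, no electrophoresis band, immunofixation negative or positive, marrow 30%: fall = 1 − 14/14 = 0%. Meets nCR, and also SD.
2. On treatment, immunofixation negative, no plasmacytoma, marrow 4%, difference 9: fall = 1 − 9/14 = 36%. Meets CR and nCR. Not PR or VGPR; not sCR, because the ratio is still abnormal.
3. As case 2 with the difference still 14: fall 0%. Still CR and nCR.
4. As case 2 with marrow 30%: nCR and SD, not CR.
5. Before the first dose, with a faint urine band of 120 mg/24 h: SD only, not nCR.

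Case 5 limits the pre-treatment finding. Entry on FLC alone means M-protein below 1 g/dL in serum and 200 mg/24 h in urine, not absent.

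**Timing.** Section 6.3.1 makes Day 1 of Cycle 1 a response assessment. Section 3.3.7.3 schedules myeloma tests at baseline and on Day 1 of each induction cycle. Two consecutive negative electrophoreses before dosing are therefore possible, although the calendar in 3.4 does not mark myeloma tests on Cycle 1 Day 1.

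**Size.** With N = 45 (10.2) and k misclassified patients, the shift is k/45: 1/45 = 2.2 points and 5/45 = 11.1 points. The range k = 0 to 5 is an assumption. If a normal ratio were required for CR, CR alone would lose the FLC-only patients whose ratio is still abnormal. VGPR+CR would lose only those among them whose difference fell by less than 90%, and ORR only those below 50%.

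Illustration with an assumed true CR count of 20 (exact 95% intervals):

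| Added patients | CR rate | 95% CI |
|---|---|---|
| 0 | 20/45 = 44.4% | 29.6 to 60.0 |
| 2 | 22/45 = 48.9% | 33.7 to 64.2 |
| 5 | 25/45 = 55.6% | 40.0 to 70.4 |

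In the interim summary, each patient removed from nCR/sCR lowers 75% by 1/20 = 5 points; 15/20 has an exact 95% interval of 50.9 to 91.3.

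**What does not move.** The toxicity rule in 10.2 (5 or more of 45) reproduces at 7.3% for a true rate of 5% and 82.5% for 15%. It uses no response data.

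**The case against.** The best defence is that 6.3.2 stands above all the categories. It refers FLC-only patients to FLC criteria, asks that both isotypes be considered, and requires confirmation on two determinations when FLC is the primary determinant of response. That shows electrophoresis alone was not meant to govern these patients. The secondary objective is also best response after 8 cycles, so a pre-dose nCR would hardly be reported as a treatment effect. All of this stands as evidence of intent. It supplies no FLC threshold for CR or nCR, so either the printed definitions apply or these patients have no rule for those categories. The cited consensus criteria may fill the gap, but that cannot be checked from the documents.

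Several stronger readings are tempting and are not supported:

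- A reader might infer that the planned rates include nCR. Neither 6.3.7 nor 10.3.1 names it.
- A reader might infer that such CRs show no fall in disease. That is wrong wherever baseline marrow plasma cells exceeded 5%, since reaching 5% or below is a documented fall. Section 2.1.1.1 sets no minimum marrow percentage, so a fall is not guaranteed either.
- A reader might infer that CR, and the tests it triggers, will be dated too early. During induction CR cannot be declared before the marrow that defines it, and marrow and PET are done at the end of cycle 8 if there is no CR.
- A reader might assume a share of FLC-only entrants, such as 5 to 15%, and a shift of up to 16 points. The documents give no share, and that shift needs every such patient to meet the full set of CR conditions.

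It is also fair that the sCR line can be read as a specific exception to the instruction to disregard FLC, and that any nCR threshold is partly a choice.

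**Conclusion.** The gap is real. The response definitions, applied as printed, allow CR without PR for an FLC-only patient, and nCR before treatment for an FLC-only patient with no electrophoresis band. The CR route needs all of its conditions together, so it is possible rather than automatic, and the documents do not show that any such patient was enrolled.

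The effect is 2.2 points per misclassified patient in a rate based on 45. For an assumed 0 to 5 patients it is at most 0 to 11 points, and less for VGPR+CR and ORR wherever the FLC difference fell enough to earn VGPR or PR anyway. The effect is confined to the secondary response outcomes and, for nCR, to the interim summary. The neurologic toxicity endpoint and the sample size are untouched.

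**What to change.** In 6.3.3.1, state that for patients followed by FLC only:

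- CR also requires a normal FLC ratio, the test already named under sCR;
- nCR is not assigned unless an FLC response criterion already in that section is met. The VGPR limb is one candidate. The documents do not dictate the threshold, so the sponsor should state which applies.

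In 6.3.2, reconcile the instruction to disregard FLC in other patients with the FLC ratio that sCR requires.

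Report CR and VGPR+CR on this rule, and give the number of patients who entered on FLC alone. Section 13.1.1 describes recruitment and carfilzomib treatment in the past tense, so data may already have been seen. In that case, report the as-written classification as a sensitivity result.

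The cost is a few sentences and no new data: 3.3.7.3 already collects FLC every induction cycle and every third cycle of extended dosing. The downsides are a possibly slightly lower CR rate and a definition clarified after enrolment, which the report should disclose.
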